#### **6.4.1.5. Management of infected human subjects**

The pre-patent period (period between infection with a parasite and the demonstration of the parasite in the body) for *P. falciparum* in man normally averages 9-12 days. In

previous studies, the pre-patent period in controls varied from 7-18 days. The shortest reported pre-patent period in man is 5 days, and the longest is 25 days [Ballou, 1987]. An immunized individual who does not have complete protection may have a prolongation of the parasite pre-patent period.

Beginning on the fifth day after their challenge (Day 27 [Visit 4]), subjects will be seen and evaluated daily by a study investigator and blood will be drawn for blood smears and PCR to check for the presence of parasites as described in Section 6.4.1.4. If fever or symptoms develop at any time, blood smears will be done more frequently (every 6 to 12 hours), and a study investigator will evaluate the subject. A confirmed positive result will be relayed immediately to the on-call investigator/study personnel by the microscopists. The infection will be treated early (i.e., as soon as parasites can be identified on thick smear) according to the treatment regimen outlined in Section 6.4.1.6. Additional PCR tests may also be performed at investigator discretion, but may not necessarily be run in real time.

Beginning on the ninth day post-challenge (Day 31 [Visit 8]), a group of hotel rooms in the local area of WRAIR will be reserved for malaria-challenged subjects. Subjects will be required to spend their nights there to allow for more rapid assessment of any potential symptoms of malaria during the hours that the study centers are closed. There will be an investigator present on-site and available for subject assessment. There will also be qualified study personnel on site 24 hours per day during the hotel phase of the study.

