**Table 6 Intervals between study visits for the P-Fx and NP-Fx groups**

Interval	Optimal length of interval*	Allowed interval**
Screening #1 → Visit 1	1 to 90 days	-
Visit 1 → Visit 2	7 days	6-8 days
Visit 1 → Visit 3 (challenge)	21 days	21-28 days
Visit 3 → Visit 22	28 days	21-35 days
Visit 22 → Visit 23	140 days	126-154 days

\*Whenever possible the investigator should arrange study visits within this interval.

\*\*Subjects may not be eligible for inclusion in the Per-Protocol Set (PPS) for analysis of immunogenicity and efficacy if they make the study visit outside this interval.

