### 11.4. Determination of sample size

The target enrollment for the MALARIA-092 study was ~130 vaccinated subjects (~26/vaccine group) and up to 30 subjects (or 4-6 per day, depending on the expected number of days of challenge) in the infectivity control group. Approximately 20 subjects in each group were expected to undergo sporozoite challenge (~100 vaccinated subjects overall). Based on past experience, an approximate 20% will refuse to participate in the booster study and there will be an approximate 20% drop-out rate in vaccinees for the booster study. With an assumed vaccine efficacy (VE) of ~68% in the primary study, there will be a minimum of ~20 subjects per group in this MALARIA-102 study. In addition, up to 24 infectivity control subjects will be newly enrolled for this study.

Assuming at least 19/20 controls and 6/20 vaccinees become positive (VE of ~68%), the trial has 99% power to detect statistically significant vaccine efficacy of each of the vaccination groups over the infectivity controls (p-value < 0.05).

The power to detect a statistically significant VE of each of the vaccination groups over the infectivity controls (p-value < 0.05) is presented in the table below:

Controls (N)	Vaccines (N)	Vaccine efficacy (%)	Protected controls (N)	Protected vaccinees (N)	Power* (%)
20	20	89	1	18	100
20	20	78	1	16	100
20	20	68	1	14	99.1
20	20	58	1	12	94.6
20	20	47	1	10	81.8

\*Two independent proportions power analysis - Test statistic: Fisher exact test

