4.2.3.1. Excluded subjects

A subject will be excluded from the PPS and the APPS analysis under the following conditions

Code	Condition under which the code is used	Visit (timepoints) where the code is applicable	Applicable for analysis set
800	Fraudulent data	All	PPS, APPS
900	Invalid informed consent or fraudulent data	All	PPS, APPS
1030	Study vaccine not administered at all	All	PPS, APPS
1040	Administration of concomitant vaccine(s) forbidden in the protocol 
 • Any investigational or non-registered vaccine other than the study vaccines used during the study period. • A vaccine not foreseen by the study protocol administered during the period starting seven days before each dose and ending seven days after each dose of vaccines administration. 	All	PPS
1070	Vaccination not according to protocol 
 • Administration not according to protocol for reason specified by the investigator, other than side, site and route. 	All	PPS, APPS
1080	Good Manufacturing Practice No-Go: Vaccine temperature deviation	All	PPS
1090	Expired vaccine administered	All	PPS
2010	Protocol violation (inclusion/exclusion criteria) 
 • Eligibility criteria not met with an impact on immunogenicity or efficacy data 	All	PPS

Code	Condition under which the code is used	Visit (timepoints) where the code is applicable	Applicable for analysis set
2040	
Administration of any medication forbidden by the protocol
 
 Any investigational or non-registered product drug other than the study vaccines used during the study period. Immunosuppressants or other immune-modifying drugs administered chronically (i.e. more than 14 days in total) during the study period. For corticosteroids, this will mean prednisone ≥ 20 mg/day (for adult subjects), or equivalent. Inhaled and topical steroids are allowed. Long-acting immune-modifying drugs administered at any time during the study period (e.g. infliximab). A vaccine not foreseen by the study protocol administered during the period starting seven days before dose and ending seven days after the dose of vaccine administration. Immunoglobulins and/or any blood products administered during Drugs known to have anti-Plasmodium properties, used during the challenge period before identification of parasitemia 	All	PPS

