5.3. Efficacy

5.3.1. Analysis of efficacy planned in the protocol

The analysis of efficacy will be performed on the PPS for analysis of immunogenicity and efficacy.

Efficacy will be assessed by comparison of *P. falciparum* parasitemia incidence and time-to-onset of *P. falciparum* parasitemia after sporozoite challenge. The analysis of the primary objective will be based on blood smears results; additional exploratory analyses will be performed based on PCR results (tertiary objectives).

Vaccine efficacy (VE) is defined as $100 * (1 - \text{Relative Risk})$. Relative risk of infection and 95% CI will be calculated.

Fisher's Exact test will be used for the comparison of *P. falciparum* parasitemia incidence after challenge between each one of the study groups (P-Fx and NP-Fx) and the infectivity control group.

Kaplan-Meier analysis will be performed on time-to-onset of *P. falciparum* parasitemia, for comparisons between each one of the study groups (P-Fx and NP-Fx) and the infectivity control group, using the log-rank statistic.

The same methodology will be applied for the evaluation of the study groups (P-Fx vs. NP-Fx) versus each other. If there are sufficient evaluable subjects (at least a 1:2 ratio between vaccinated and control groups) to draw some conclusions, descriptive analyses based on initial group assignment versus control will be performed.

All statistical tests will be two-tailed at 5% significance level.

Risk periods

For the analyses of time-to-onset of parasitemia (Kaplan-Meier and log-rank), time-at-risk will start on first day of challenge. Time-at-risk will be censored on Visit 22 (Day 50; 28 days post-challenge), drop-out date, start date of anti-malarial treatment or date meeting an endpoint, whichever occurs first. Time-at-risk will be calculated as: censor date – challenge date + 1.

For the analysis of proportion affected (relative risk), all subjects included in the PPS for analysis of immunogenicity and efficacy will be considered at risk of infection and no censoring or elimination will be applied for subjects not completing the entire protocol defined post-challenge follow-up (Day 50; 28 days post challenge).

Case definition

The following will be used as case definition of *P. falciparum* infection:

Asexual blood stage *P. falciparum* parasite density > 0 detected by blood slide reading (or PCR for tertiary objectives).

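### The primary relative risk counts challenged subjects who leave without a positive slide as non-cases, which can bias VE upward if vaccinees become positive later than controls; no sensitivity analysis is planned

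*SAP*

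**What the plan says.** **Relative risk.** Protocol 11.9 and SAP 5.3.1 (Risk periods) treat all PPS subjects as at risk and state that "no censoring or elimination will be applied for subjects not completing the entire protocol defined post-challenge follow-up". The case definition in SAP 5.3.1 requires parasites on a blood slide (PCR for the tertiary objectives). Read together, an early leaver with no positive slide is a non-case in the denominator.

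**Time to onset.** The same section censors at Visit 22, drop-out, start of anti-malarial treatment or the endpoint, whichever is first.

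**Timing.** Protocol 6.4.1.5 gives control onset in previous studies as 7 to 18 days and the longest reported onset in man as 25 days. It adds: "An immunized individual who does not have complete protection may have a prolongation of the parasite pre-patent period". No length is given for that prolongation.

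**Slides.** They are daily from 5 to 18 days after challenge, then at 20, 22, 24, 26 and 28 days. Telephone symptom screening may replace those of the visits on Days 42 to 48 that fall on a weekend.

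**Analysis sets.** SAP 4.2.3.1, code 2040, removes users of drugs with anti-*Plasmodium* "properties, used during the challenge period before identification of parasitemia". It applies to the PPS only, as do codes 2090 (blood sample schedule) and 2100 (anti-CS results). The interim analysis uses the Adapted PPS, and SAP 7.1 says its results will inform a decision on future field trials.

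Neither document plans an imputation, bounding or other sensitivity analysis for non-completers.

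**The concern.** The crude proportion treats not observed as not infected. That is harmless if everyone is followed to Day 50 with all slides taken, or if the two arms lose the same share of future cases. It is not harmless if onset is later in vaccinees. From about day 18 most control infections should already be on slide, while some vaccinee infections may still be to come. Loss or a missed slide in that window then hides mainly vaccinee cases, and VE reads too high.

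Two further consequences follow.

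- The SAP's pooled P and NP groups (SAP 2) are defined by slide status in this challenge. A vaccinee who left early would enter P and carry the misclassification into the immune-marker comparisons and logistic models of SAP 5.4.2.
- Code 2090 cites the table that holds the Visit 22 window, and code 2100 can be read as requiring anti-CS results at every visit. Either may remove a vaccinee who misses Day 50, which conflicts with the no-elimination rule. Controls give no antibody samples (Protocol Table 5), so the same loss could be handled differently by arm.

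**Working it through.** **Inputs.** Protocol 11.4: "Assuming at least 19/20 controls and 6/20 vaccinees become positive (VE of ~68%), the trial has 99% power", 20 per group, with the table note "Test statistic: Fisher exact test". SAP 5.3.1: VE = 100 × (1 − RR), and "All statistical tests will be two-tailed at 5% significance level". No drop-out rate is given for the 28 days after challenge, so I take 5 to 20% as an assumed range.

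**1. The plan's own figures.** VE = 1 − (6/20)/(19/20) = 68.4% (log-RR 95% CI 37.9 to 84.0), as stated. Exact Fisher power by full enumeration at two-sided 0.05 is 99.7%, against the stated 99% (99.1% in the table). The table's three lowest rows (99.1, 94.6, 81.8) reproduce exactly at two-sided 0.025; at 0.05 they are 99.7, 97.4 and 89.4. The table is therefore conservative, and this does not affect the point.

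**2. One misclassified vaccinee.** (1/20)/(19/20) = 1/19 = 5.3 points of VE. Two turn a true 8/20 (57.9%) into 6/20 (68.4%). Four turn a true 10/20 (47.4%) into 68.4%, a gap of 21 points.

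**3. Observed 6/20 vs 19/20, with k of the 14 slide-negative vaccinees lost early.**

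| k | Counted as non-cases (plan) | Excluded | Counted as infected |
|---|---|---|---|
| 1 | 68.4% | 1 − (6/19)/0.95 = 66.8% | 1 − (7/20)/0.95 = 63.2% |
| 2 | 68.4% | 1 − (6/18)/0.95 = 64.9% | 1 − (8/20)/0.95 = 57.9% |
| 4 | 68.4% | 1 − (6/16)/0.95 = 60.5% | 1 − (10/20)/0.95 = 47.4% |

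Fisher p is at most 0.0033 throughout. The excluded column is also what the plan gives if code 2090 or 2100 removes these vaccinees, so that ambiguity alone is worth 1.7, 3.5 or 7.9 points. With controls complete, a 28-day Kaplan-Meier risk ratio falls between the first two columns: it equals exclusion if all losses precede the first event in the group, and the crude figure if all follow the last.

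On the table's weakest row (10/20 vs 19/20) with four lost, VE is 47.4% as planned (p = 0.003), 34.2% if they are excluded (p = 0.030) and 26.3% if they are counted as infected (p = 0.091).

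**4. Direction.** If the same fraction d of future cases is lost in both arms, RR = 0.30(1 − d)/[0.95(1 − d)] and VE stays at 68.4% for any d. If 1, 2 or 4 controls who would have been infected are lost, VE falls to 1 − 0.30/0.90 = 66.7%, 1 − 0.30/0.85 = 64.7% or 1 − 0.30/0.75 = 60.0%.

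**5. Size under random loss.** Suppose drop-out runs at a constant rate reaching d by day 28, and vaccinee onset is delayed by δ days. Then VE = 1 − (0.30/0.95)(1 − d)^(δ/28). For δ = 3 to 6 (assumed):

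- d = 5%: 68.6 to 68.8%
- d = 10%: 68.8 to 69.1%
- d = 20%: 69.2 to 69.9%

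If instead loss occurs only after day 18 and a share s of vaccinee infections falls that late, VE = 1 − 0.30(1 − ds)/0.95. For s = 10 to 50% (assumed) this gives 68.6 to 69.2% at d = 5% and 69.1 to 71.6% at d = 20%. Against 68.4%, the gain is about 0.2 to 3 points.

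**6. Why 21 points is a ceiling.** It needs 4 of 20 lost after challenge and all four truly infected. Protocol 11.4 says "there will be an approximate 20% drop-out rate in vaccinees for the booster study", but that rate is not specific to the 28-day window. It also appears to be netted out already in reaching about 20 per group: 100 × 0.8 × 0.8 = 64, and 64 × 0.32 = 20.5 previously unprotected subjects. Taking another 4 from 20 would apply the same 20% twice.

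**The case against.** The case against is substantial, and part of it stands.

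- **Early treatment.** A reader might infer that subjects treated before a positive slide count as protected in the primary analysis. They do not: the PPS definition and code 2040 remove them. The planned trigger for treatment is a positive smear, so such cases should be few. The gap is confined to the Adapted PPS.
- **Who is at risk late.** A reader might infer that only vaccinees are at risk late, so that VE must be inflated. Control onset ran to day 18, 25 days has been reported, and step 4 shows that bias in either direction is possible.
- **Visit 22 window.** Table 6 allows 21 to 35 days for "Visit 3 → Visit 22", which might suggest that slides may stop at day 21. That row is a visit tolerance; slides are scheduled separately up to 28 days, with Visit 21 at 26 days. What remains is that individual late slides can be missed, including by weekend telephone contact.
- **Safeguards.** A hotel phase from day 9 to day 18, active tracing and telephone follow-up make early loss unlikely. Withdrawals are tabulated by reason.
- **Two methods.** Handling a drop-out differently in a proportion and in a survival curve is ordinary practice, not a contradiction in itself. But the planned Kaplan-Meier analysis feeds a log-rank test, and VE is defined only from the relative risk, so no VE estimate allows for incomplete follow-up.
- **Status.** Both documents call all analyses descriptive, which lowers the stakes. It does not remove the need for a sound estimate.

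**Conclusion.** The rule is explicit, and its effect is that non-completers without a positive slide are non-cases in the primary VE. Upward bias is plausible because vaccinee onset may be later, but it is conditional on who is lost and when. Each misclassified vaccinee is worth 5.3 points; random loss is worth about 0.2 to 3 points, given the assumed 5 to 20% loss and the assumed onset timing. The 21-point figure is not an expectation. At the design effect the nominal conclusion survives every scenario in step 3; at the weakest row of the power table it could change only if all four lost vaccinees were infected.

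In the Adapted PPS, subjects given an anti-malarial before a positive slide can remain as non-cases in the analysis that informs field-trial decisions. The documents give no expected number of them.

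This is an inexpensive improvement, not a flaw that invalidates the primary analysis.

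**What to change.** 1. Report VE from the ratio of 28-day Kaplan-Meier risks, 1 − KM(28), in each group beside the crude relative risk. State the time point as 28 days post-challenge; the SAP's time-at-risk formula adds one day, so this is time 29 on its scale.
2. Add a bounding table for non-completers without a positive slide. Lower bound: lost vaccinees counted as infected and lost controls as uninfected. Upper bound: the converse.
3. Reconcile the no-elimination rule with codes 2090 and 2100. Say whether a vaccinee who misses Day 50 stays in the efficacy analysis, and whether code 2100 means no anti-CS result at any visit or not a complete set.
4. In the Adapted PPS, either exclude anti-malarial use before a positive slide, as in the PPS, or censor it in the Kaplan-Meier-based estimate. Because such treatment may be prompted by symptoms, that censoring may be informative, so add counting these subjects as infected as a sensitivity analysis. It should not be the main rule, because it departs from the slide-only case definition.

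The cost is a few lines of SAP text and one extra table. Reported VE may be slightly less favourable.

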5.4. Immunogenicity

5.4.1. Analysis of immunogenicity planned in the protocol

The analysis of immunogenicity will be performed on the PPS for analysis of immunogenicity and efficacy.

For each group, at each timepoint where a blood sample is collected:

- The percentage of subjects with seropositive levels of anti-CS (proportion of subjects with anti-CS antibody concentrations ≥ 1.9 EU/mL) with 95% CI will be determined at specified blood sampling timepoints. Anti-CS antibody concentrations will be summarized by GMC. Anti-CS antibody concentrations will be displayed using reverse cumulative curves (RCCs). Similar analysis will be performed for the anti-full length CS protein (proportion of subjects with anti-CS antibody titers ≥ 200 1/DIL) and anti-C-term antibodies (proportion of subjects with anti-CS antibody concentrations ≥ 100 Endpoint Titer).
- The percentage of subjects with seroprotection levels of anti-HBs (anti-HBs antibody concentrations ≥ 10 mIU/mL) with 95% CI will be determined at specified blood sampling timepoints. Anti-HBs antibody concentrations will be summarized by GMC. Anti-HBs antibody concentrations will be displayed using RCCs.

Anti-CS, anti-full length CS protein and anti-CS avidity index will be summarized by mean, SD, median and quartile and box and whiskers plots will be generated.

5.4.2. Additional considerations

In addition to the previous analyses, the immunogenicity analyses will be performed per protection status (P and NP) overall (pooled vaccine groups) and within each vaccine group.

Comparisons of the log-transformed means of anti-CS antibodies (repeated, full length, C-Term and avidity index), post vaccination and at the time of the challenge and for P vs NP (Student 2-Sample Test) will be performed.

Exploratory analyses using logistic regression models will be evaluated to describe the relationship between immune read outs and the probability of infection (P vs NP). Explanatory variables will include all or a part of available immune read outs at time of analysis (anti-CS, anti-full length CS protein, avidity index).

In a first step, immune responses will be plotted by group and protection status as well as cross-tabulated to understand potential correlation structures. Then, relevant models will be constructed to evaluate what are the independent predictors of protection, both pooled over the treatment groups (is/are there a generic driver(s)?) and by treatment schedule/including interactions (is protection mediated through different mechanisms between schedules?).

For the study groups and the pooled groups, we will also generate graphs to represent the evolution of the immunogenicity over the time.

5.5. Analysis of safety and reactogenicity

5.5.1. Analysis of safety and reactogenicity planned in the protocol

The analysis of safety will be performed on the ITTS.

For the P-Fx and NP-Fx groups:

- The percentage of subjects with at least one local AE (solicited and unsolicited), with at least one general AE (solicited and unsolicited) and with any AE during the 7-day or 21-day follow-up period after the booster Fx dose will be tabulated with exact 95% CI. Same computations will be done for grade 3 AEs, for any AEs considered related to vaccination and for any grade 3 AEs considered related to vaccination.
- The percentage of subjects reporting each individual solicited local AE (any grade and grade 3) and each individual solicited general AE (any grade, grade 3, any related, grade 3 related, resulting in medically attended visit) during the 7-day follow-up period (Days 1-7) after the booster Fx dose will be tabulated for each group, with exact 95% CI.
- For fever (defined as temperature $\geq 37.5^{\circ}\text{C}/99.5^{\circ}\text{F}$ for oral, axillary or tympanic route), the number and percentage of subjects reporting fever by half degree ($^{\circ}\text{C}$) cumulative increments during the first seven days (Days 1-7) after the booster Fx dose will be tabulated. Similar tabulations will be performed for any fever with a causal relationship to vaccination and grade 3 ($> 39.0^{\circ}\text{C}$) causally related fever. The maximum temperature reported over the 7-day follow-up period will be tabulated.
- The percentage of subjects reporting unsolicited AEs within 21 days (Days 1-21) after the booster Fx dose will be tabulated by group and by MedDRA preferred term with exact 95% CI. Similar tabulation will be done for grade 3 unsolicited AEs, for any causally related unsolicited AEs and for grade 3 causally related unsolicited AEs.
- The percentage of subjects using concomitant medication (any medication, any antipyretic and any prophylactic medication, respectively) during the 7-day follow-up period after vaccination will be summarized by group.

For all subjects:

- The percentage of subjects reporting AEs during 29 days after the sporozoite challenge (Day 22-Day 50) will be tabulated by group and by MedDRA preferred term with exact 95% CI. Similar tabulation will be done for grade 3 unsolicited AEs, for any causally related unsolicited AEs and for grade 3 causally related unsolicited AEs post challenge.

- The percentage of subjects reporting AEs of specific interest (meningitis and pIMDs) from Day 1 until last study visit (Day 190) (for P-Fx and NP-Fx groups)/from the day of challenge until last study visit (Day 50) (for infectivity control group), classified by MedDRA preferred term level, will be tabulated with exact 95% CI.
- The percentage of subjects reporting SAEs (all, fatal, related) occurring from Day 1 until last study visit (Day 190) (for P-Fx and NP-Fx groups)/from the day of challenge until last study visit (Day 50) (for infectivity control group), classified by the MedDRA preferred term level will be tabulated with exact 95% CI.
- Subjects reporting pregnancies will be described.
- The percentage of subjects reporting an AE or SAE leading to withdrawal from study from Day 1 until last study visit (Day 190) (for P-Fx and NP-Fx groups)/from the day of challenge (for infectivity control group) until last study visit (Day 50), classified by MedDRA preferred term level, will be tabulated with exact 95% CI.
- The percentage of subjects using concomitant medication during the entire sporozoite challenge (Days 22-50) will be summarized by group.

Biochemistry (ALT, AST and creatinine) and hematological (hemoglobin, WBC and platelets) laboratory values will be presented by visit according to toxicity grading scales and tabulated by group. The normal ranges and toxicity grading for laboratory safety parameters used in this study are presented in the following table.

Table 3 Toxicity grading scales for blood testing

Adverse event	Intensity grade	Intensity*
Hemoglobin (males)	Normal range	≥ 12.5 g/dl
	1	< 12.5 but ≥ 11.0 g/dl
	2	< 11.0 but ≥ 10.0 g/dl
	3	< 10.0 g/dl
Hemoglobin (females)	Normal range	≥ 11.5 g/dl
	1	< 11.5 but ≥ 10.5 g/dl
	2	< 10.5 but ≥ 9.5 g/dl
	3	< 9.5 g/dl
Increase in leukocytes (WBC)	Normal range	≤ 10799 cells/mm ³
	1	10800 - 15000 cells/mm ³
	2	15001 - 20000 cells/mm ³
	3	> 20001 cells/mm ³
Decrease in leukocytes (WBC)	Normal range	≥ 3200 cells/mm ³
	1	2500 - 3199 cells/mm ³
	2	1500 - 2499 cells/mm ³
	3	< 1500 cells/mm ³
Decrease in platelets	Normal	≥ 140000 cells/mm ³
	1	125000 - 139000 cells/mm ³
	2	100000 - 124000 cells/mm ³
	3	< 100000 cells/mm ³
Alanine Aminotransferase	Normal range	Below ULN (60 U/l for males; 40 U/l for females)
	1	1.1 - 2.5 x ULN
	2	2.6 - 5 x ULN
	3	> 5 x ULN
Aspartate Aminotransferase	Normal range	Below ULN (40 U/l for males; 35 U/l for females)
	1	1.1 - 2.5 x ULN
	2	2.6 - 5 x ULN
	3	> 5 x ULN
Creatinine (males)	Normal range	≤ 1.39 mg/dl
	1	1.4 - 1.79 mg/dl
	2	1.8 - 2.0 mg/dl
	3	> 2.0 mg/dl
Creatinine (females)	Normal range	≤ 1.29 mg/dl
	1	1.3 - 1.69 mg/dl
	2	1.7 - 1.9 mg/dl
	3	> 1.9 mg/dl

ULN: upper limit of normal range

* Grading scale adapted from [FDA guidance for industry toxicity grading scale for healthy adult and adolescent volunteers enrolled in preventive vaccine clinical trials (September 2007)].

